## 9.0 STATISTICAL CONSIDERATIONS

### 9.1 Sample Size and Study Duration

For both strata, we will use an information-based design and the final analysis will be conducted when the specified number of events are attained. For Stratum 1, we expect to enroll 65 eligible and evaluable patients in approximately 3 years and we expect follow each patient for at least 1 year before the expected number of events (i.e., 35) is observed. For Stratum 2, we plan to enroll 30 eligible patients during the same period. The number of events needed to achieve the specified power under the design assumptions for this stratum is 13. We expect that we will need to follow the last patient for 3 years before 13 events are observed. Only patients who pass the screening process and start protocol defined treatment within 31 days (34 days for veliparib) of surgery will be eligible and evaluable for assessing efficacy. Patients who pass the screening process but are not able to start treatment within 31 days (34 days for

veliparib) of surgery will not be eligible and will be replaced. The maximum projected sample size for this study is 115 to account for ineligible/inevaluable patients. We expect we will need to molecularly screen up to 220 subjects to achieve the targeted sample size of eligible and evaluable patients.

Stratum 1 is the primary stratum that will control accrual for this trial. If accrual to Stratum 1 is completed and 30 patients have not yet been enrolled on Stratum 2, we will consult the COG Leadership and COG DSMC regarding whether accrual to Stratum 2 should continue.

#### 9.1.1 Closure of Stratum 1 IDH (Wild-Type Cohort) Effective January 24, 2020

Stratum 1 of ACNS1721, for patients with IDH wild-type HGG, was closed to accrual as of January 24, 2020. Closure of this stratum was based on the results of a planned interim analysis. The available data from the first 22 subjects at the time of interim analysis suggested that the hypothesized superior outcome for the ACNS1721 treatment compared to the historical controls was unlikely. There were no concerns regarding excessive toxicities on this protocol.

## 9.2 **Study Design**

This study will evaluate the efficacy of the planned regimen in two molecularly defined pediatric newly-diagnosed HGG subgroups. Stratum 1 will enroll patients who are wild-type with respect to H3 K27M, *BRAF*, and *IDH1/2*. Stratum 2 will enroll patients whose tumors are positive for *IDH1/2* mutation and wild-type for *BRAF* and H3 K27M. The primary efficacy endpoint is EFS in both strata and the efficacy of the regimen used in this study will be assessed by comparing the stratum-specific EFS outcome to clinically and molecularly matched historical controls. These historical controls have been derived from Korshunov et al., and from ACNS0822 for Stratum 1 and from Korshunov et al., ACNS0822, ACNS0423, the recent *Cell* meta-analysis paper, and the HERBY trial for Stratum 2. These historical data sets that will be used for these comparisons have already been extracted and will be stored in the COG file share for this study for ease of access at future analysis points. These data will not be updated as these cohorts are quite mature at the time of the design of this study.

[figure not shown]
### **Stratum 1:**

The following is a description of the historical control cohort used in this stratum.

[figure not shown]
ACNS0822: ACNS0822 is the most recently completed COG phase 2 frontline HGG trial. The phase 2 trial enrolled 90 eligible patients and while patients were randomized among 3 regimens, the results did not indicate any difference among these arms. Thus, for the purposes of this study, the data from these 3 regimens will be combined. Of the 90 eligible patients, 62 had adequate biology information to be included in our analyses and 34 met the molecular eligibility criteria defined as no H3 K27M mutant, *IDH1/2* mutant, or *BRAF*V600 mutant tumors.

Korshunov et al. Cohort (aka Heidelberg Cohort): The second cohort which will be used to construct our historical control group for Stratum 1 is derived from the cohort analyzed by Korshunov et al. This cohort included 140 patients who were aged 3 years and older, had tumors outside the brainstem and had non-disseminated disease. Of these, 84 (60%) were also negative for H3 K27M, *IDH*, and *BRAF* mutations. This group of 84 subjects will be included in the historical control cohort.

To determine if there are systematic differences between these two cohorts that may preclude us from combining them for the purpose of constructing a larger historical control cohort for the proposed trial, we analyzed both of these cohorts simultaneously. The plot below displays the PFS distribution by cohort and suggests no notable differences between these two data sets. The logrank p-value associated with the PFS comparisons is 0.296. There were no secondary malignancies reported as the first event in these cohorts so EFS and PFS are the same.

Combining these data into one dataset (n=118), we obtain the following PFS curve which we propose to use as our historical control cohort against which the outcome of the current trial will be compared. This cohort contains 91 progression events with 1-, 2- and 5- year PFS estimates ( $\pm$ se) given as 42.6% ( $\pm$ 4.6%), 22.2% ( $\pm$ 4.2%), and 12.5% ( $\pm$ 4.6%), respectively.

[figure not shown]

Using the approach proposed by Korn and Freidlin which was further refined by Wu and Xiong, we will employ a group sequential approach based on a 1-sided log rank test to

estimate the sample size and monitor for futility in this stratum. Using the methodology described in Wu and Xiong and the empirical Kaplan-Meier estimate to model the EFS distribution, the design proposed here requires 65 patients to detect a HR=0.55 with 5% type I error and 90% power. HR=0.55 translates to approximately 20% improvement in PFS at 1 and 2 years. The design also stipulates that all patients will be followed for at least 1 year post-accrual completion with an estimated accrual duration of approximately 3 years. Interim monitoring for futility only will be done using an alpha-spending approach based on the gamma family with  $\gamma=4$ . The expected number of PFS events (total information) during the entire duration of the trial is 35 and we will conduct the first interim analysis starting with the 10th failure, which is expected to occur approximately 2 years after accrual initiation. Subsequently, interim analyses will be conducted approximately annually corresponding with the DSMC reports. We expect to conduct no more than 3 interim analyses.

[figure not shown]
**Stratum 2:**

Stratum 2 will enroll patients with *IDH* mutant tumors. Of note, *IDH* mutations are generally mutually exclusive with H3 K27M and *BRAF* mutations. Given the fact that *IDH* mutations generally occur in patients who are in their teenage or early 20s, eligibility is extended to 25 years in this stratum. Due to the rarity of these tumors, historical data are somewhat sparse. In the Heidelberg cohort, only 10 (7.1%) patients had *IDH* mutations among the 140 patients who were aged 3 years and older, had tumors outside the brainstem and had non-disseminated disease. In the ACNS0822 cohort, 8/62 (12.9%) had *IDH* mutations. *IDH* information was also available from a subset of patients treated on the ACNS0423 study. ACNS0423 was a phase 2 study which preceded ACNS0822. This study enrolled 108 eligible patients with similar eligibility criteria and treated them with temozolomide + RT followed by 6 cycles of temozolomide + lomustine. Among these, *IDH* mutations were assessed in 43 patients and 7 (16.3%) were identified as *IDH* positive. We were also able to obtain data from 6 additional *IDH* patients included in the recent *Cell* meta-analysis paper and 4 patients from the HERBY study (personal communication, [name]). The PFS distributions of *IDH* mutated patients from these 5 studies are given in the Kaplan-Meier (KM) plot below. While there is some variability, these PFS distributions are not statistically different from each other (logrank p-value=0.325). Similarly here as well, PFS and EFS distributions are the same.

We will use the combined group from these 5 cohorts as our historical control. This cohort includes 35 patients and 18 PFS events for patients whose median age is 16.9 years (range 11.7–28). The KM plot of the combined cohort is given below. The estimated 1, 2, and 5 year PFS estimates ( $\pm$ se) are 85.4% ( $\pm$ 6.05%), 61.1% ( $\pm$ 8.5%), and 35.8% ( $\pm$ 11.4%), respectively.

PFS Distribution of Combined Historical Cohort of IDH Mutated Patients

Using the same methodology as in Stratum 1, we will employ a group sequential approach based on a 1-sided logrank test to estimate the sample size and monitor for futility in this stratum. Using the methodology described in Wu and Xiong and the KM estimate to model the PFS distribution, the design proposed here requires 30 patients to detect a HR=0.45 with 10% type I error and 80% power. HR=0.45 translates to approximately 8% improvement in PFS at 1 year and 19% at 2 years. The design also stipulates that all patients will be followed for at least 3 years post-accrual completion with an estimated accrual duration of 2–3 years. Interim monitoring for futility only will be done using an alpha-spending approach based on the gamma family with  $\gamma = -4$ . The expected number of PFS events (total information) during the entire duration of the trial is 13 and we will conduct the first interim analysis starting with the 5th failure which is expected to occur at the end of accrual if the treatment is effective. Otherwise if the treatment has the same efficacy as historical controls, we expect to observe 6 events 2–2.5 years after actual initiation. Subsequently, interim analyses will be conducted approximately annually corresponding with the DSMC reports. We expect to conduct approximately 3 interim analyses.

### 9.3 Methods of Analysis

For both strata, the primary analysis for EFS will be based on a 2-sample, 1 sided logrank test. For each stratum we will also consider Cox models that incorporate known prognostic factors as feasible including resection status (GTR vs. < GTR) and tumor grade (Grade 3 vs. 4), etc. to ensure that these variables do not have undue influence on the overall outcome. For patients with measurable disease at baseline, we will also report the objective response rate.

**9.4 Evaluability for Toxicity and Efficacy Assessments**

All patients who start radiation therapy and receive at least 1 dose of veliparib will be evaluable for toxicity and efficacy assessments. The latter refers to the primary endpoint of EFS and secondary endpoints of objective response and OS.

**9.5 Analysis Plan for Exploratory Objectives**

For the biology/molecular data, we will provide a frequency table summarizing the number of patients with each aberration/alteration detected in germline and/or tumor samples. For longitudinal plasma samples used to assess circulating tumor DNA, we will summarize the percentage of patients with samples as well as display/summarize any changes in molecular markers. When feasible we will explore the association of these aberrations with EFS/OS and objective response rates via Cox models and fisher exact tests, respectively. We will also explore associations between genetic variants and clinical/demographic variables including age, resection status, histology, etc. For analyses exploring associations of a large number of potential markers with clinical outcome, we will utilize false discovery rate approaches in order to control family-wise error rate.

**9.6 Gender and Minority Accrual Estimates**

The total estimated sample size of eligible and evaluable patients for this study is 95 patients (65 in Stratum 1 and 30 in Stratum 2). In order to accommodate for possible ineligible and inevaluable patients, we expect that the maximum number of enrolled patients will be 115. The gender and minority distribution of the study population is expected to be:

DOMESTIC PLANNED ENROLLMENT REPORT					
Racial Categories	Ethnic Categories				Total
	Not Hispanic or Latino		Hispanic or Latino		
	Female	Male	Female	Male	
American Indian/ Alaska Native	0	0	0	0	0
Asian	2	4	0	0	6
Native Hawaiian or Other Pacific Islander	1	0	0	0	1
Black or African American	5	5	0	1	11
White	36	40	5	10	91
More Than One Race	0	0	0	0	0
Total	44	49	5	11	109

INTERNATIONAL (including Canadian participants) PLANNED ENROLLMENT REPORT					
Racial Categories	Ethnic Categories				Total
	Not Hispanic or Latino		Hispanic or Latino		
	Female	Male	Female	Male	
American Indian/ Alaska Native	0	0	0	0	0

Asian	0	0	0	0	0
Native Hawaiian or Other Pacific Islander	0	0	0	0	0
Black or African American	0	0	0	0	0
White	5	1	0	0	6
More Than One Race	0	0	0	0	0
Total	5	1	0	0	6

This distribution was derived from ACNS0822 and ACNS0423, the two previous COG studies conducted in this patient population.

## 10.0 EVALUATION CRITERIA

### 10.1 Common Terminology Criteria for Adverse Events (CTCAE)

This study will utilize version 5.0 of the CTCAE of the National Cancer Institute (NCI) for toxicity and performance reporting. A copy of the CTCAE version 5.0 can be downloaded from the CTEP website

([http://ctep.cancer.gov/protocolDevelopment/electronic\\_applications/ctc.htm](http://ctep.cancer.gov/protocolDevelopment/electronic_applications/ctc.htm)).

Additionally, toxicities are to be reported on the appropriate case report forms.

Please note: 'CTCAE v5.0' is understood to represent the most current version of CTCAE v5.0 as referenced on the CTEP website (i.e., v5.02 and all subsequent iterations prior to version 6.0).

[figure not shown]
### 10.2 Methodology to Determine Tumor Measurement

Tumor dimensions are determined by measurement of the longest tumor dimension and its perpendicular for each target lesion. Regarding MRI imaging, the radiologist may select whatever sequence best highlights the tumor (T1 enhanced or T2 weighted or FLAIR images) and the same sequence should be used for serial measurements. Response determination will be based on a comparison of an area (W x T – see below) between the baseline assessment and the study date designated in the follow-up Report Form. Reports for the follow-up exams should reiterate the measurements obtained at baseline for each target lesion. Non-target lesions or newly occurring lesions should also be enumerated in these reports, and changes in non-target lesions should be described.

Tumor response criteria are determined by changes in size using the longest tumor dimension, and its perpendicular. Either T1, T2 weighted/FLAIR images are used – whichever gives the best estimate of tumor size. The following section describes the methodology.

1. For MRI imaging, the longest diameter can be measured from the axial plane or the plane in which the tumor is best seen or measured, provided the same plane is used in follow ups. This longest measurement of the tumor is referred to as the width (W).

2. The perpendicular measurements should be determined – transverse (T) measurement, perpendicular to the width in the selected plane.

**COG GUIDELINE: TUMOR SIZE MEASUREMENT BASED ON CROSS-SECTIONAL IMAGING**

- A, B, C, D, & E are contiguous parallel slices in the X-Y plane (usually axial) showing the tumor
- W and T are the maximal perpendicular diameters on the slice (C in this example) showing the largest surface area
- Tumor length in the Z-axis (L) (perpendicular to X-Y plane) can be obtained either by the [a] (difference in table position of the first and last slices showing the tumor + one slice thickness), or [b] the product of (slice thickness + gap) and the number of slices showing the tumor

**RELATIONSHIP BETWEEN CHANGE IN SINGLE DIAMETER (RECIST) AND PRODUCT OF TWO DIAMETERS (WHO)**  
(Modified from Appendix II, Table 2, JNCI 92:213, 2000)

Response	Diameter, 2R	Product, (2R) 
Decrease	30%	50%
	50%	75%
	Increase	Increase
Disease Progression	12%	25%
	20%	44%
	25%	56%
	30%	69%

3. The cystic or necrotic components of a tumor are not considered in tumor measurements. Therefore only the solid component of cystic/necrotic tumors should be measured. If cysts/necrosis compose the majority of the lesion, the lesion may not be “measurable”.

Options:

- if the cyst/necrosis is eccentric, the W and T of the solid portion should be measured, the cyst/necrosis excluded from measurement
- if the cyst/necrosis is central but represents a small portion of the tumor (< 25%), disregard and measure the whole lesion
- if the cyst/necrosis is central but represents a large portion of the tumor, identify a solid aspect of the mass that can be reproducibly measured

4. Leptomeningeal tumor spread is usually not a target lesion, and usually cannot be measured accurately. Presence and location of leptomeningeal tumor spread should be noted and change in extent/thickness assessed on follow up studies. **Note that patients with leptomeningeal disease are not eligible for enrollment on this study.**

5. Overall Response Assessment

The overall response assessment takes into account response in both target and non-target lesion, and the appearance of new lesions, where applicable, according to the criteria described in the table below. The overall response assessment is shown in the last column, and depends on the assessments of target, non-target, and new lesions in the preceding columns.

Target Lesions	Non-target Lesions	New Lesions	Overall Response
CR	CR	No	CR
CR	IR/SD	No	PR
PR	CR, IR/SD	No	PR
SD	CR, IR/SD	No	SD
PD	Any	Yes or No	PD
Any	PD	Yes or No	PD
Any	Any	Yes	PD

CR – Complete Response

PR – Partial Response

SD – Stable Disease

PD – Progressive Disease

IR – Incomplete Response

The sections that follow discuss the selection and evaluation of each of these types of lesions.

### 10.3 Selection of Target and Non-Target Lesions

- a. For most CNS tumors, only one lesion/mass is present and therefore is considered a “target” for measurement/follow up to assess for tumor progression/response. Note that patients with M+ disease are not eligible for enrollment on this study.
- b. If multiple measurable lesions are present, up to 3 should be selected as “target” lesions. Target lesions should be selected on the basis of size and suitability for accurate repeated measurements. All other lesions will be followed as non-target lesions.
- c. The lower size limit of the target lesion(s) should be at least twice the thickness of the slices showing the tumor to decrease the partial volume effect (e.g., 8 mm lesion for a 4 mm slice).
- d. Any change in size of non-target lesions should be noted, though does not need to be measured.

#### 10.4 Response Criteria for Target Lesions

1. Response criteria are assessed in 2 dimensions – the product of W x T.
2. To assess response/progression, the ratio is calculated:

$$\frac{W \times T \text{ (current scan)}}{W \times T \text{ (reference scan)}}$$

3. Development of new disease or progression in any established lesions is considered progressive disease, regardless of response in other lesions – e.g., when multiple lesions show opposite responses, the progressive disease takes precedence.
4. Response Criteria for target lesions:

**Complete Response (CR):** Disappearance of all target lesions.

**Partial response (PR):**  $\geq 50\%$  decrease in the sum of the products of the two perpendicular diameters of target lesions, compared to baseline measurement.

**Stable Disease (SD):** Neither sufficient decrease in the sum of the products of the two perpendicular diameters of all target lesions to qualify for PR (taking as reference the initial baseline measurements), nor sufficient increase in a single target lesion to qualify for PD, (taking as reference the smallest disease measurement since the treatment started).

**Progressive Disease (PD):**  $\geq 25\%$  increase in the product of perpendicular diameters of ANY target lesion, taking as reference the smallest product observed since the start of treatment (see exception below); OR the appearance of one or more new lesions, OR worsening neurologic status not explained by causes unrelated to tumor progression (e.g., anticonvulsant or corticosteroid toxicity, electrolyte disturbances, sepsis, hyperglycemia, presumed post-therapy swelling, etc.) PLUS any increase in tumor cross-sectional area (or tumor volume).

However, because radiotherapy may be associated with transient, reversible swelling during or within the first 3 months after completion of RT, there may be a lag time between the initiation of therapy and maximal anti-tumor effect. Removing a patient from protocol therapy as soon as tumor area increases by 25% may result in the treatment being terminated prematurely. It is quite possible that if these patients were maintained on protocol therapy, their disease might eventually stabilize and even regress.

**Therefore, patients will not be considered to have progressive disease and will not be removed from protocol therapy for radiographic worsening secondary to local tumor enlargement (LTE), defined as increase in maximal bi-dimensional tumor area of 25% or more but less than 50%, and with no new lesions on any MRI performed within 3 months from completion of RT (i.e., on the required MRI 4 weeks after completing RT, or the scan performed prior to Cycle 3 of the Maintenance). Thus, during and for 3 months after completion of RT, patients should only be removed from protocol therapy for progressive disease if there is 50% or more**

increase in tumor area (with or without neurological worsening), OR if there is the appearance of one or more new lesions on the MRI outside the radiation port.

The criteria for progressive disease as defined above will commence with the required brain MRI scans done more than 3 months after completion of RT (i.e., prior to Cycle 3 of therapy, or scans done for suspected progression more than 3 months after completion of RT). Patients whose tumors meet these criteria will be removed from protocol therapy.

Local progression is defined as progression of known residual tumor or the appearance of tumor at known prior sites of disease that were at some point without evidence of disease. Distant progression is defined as the appearance of tumor at sites other than known prior sites of disease. Distant progression most often occurs in the subarachnoid space and may occur at any point within the neuraxis. Although rare, extra-CNS metastasis represents distant failure. Combined local and distant progression is defined when evaluation of the entire neuraxis reveals local and distant progression.

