### 4.1 **Overview of Treatment Plan**

This study will evaluate the efficacy of the proposed regimen in two molecularly defined pediatric newly-diagnosed HGG subgroups. Stratum 1 will enroll patients who are wild-type with respect to H3 K27M, *BRAF*, and *IDH1/2*. Stratum 2 will enroll patients who are positive for either *IDH1/2* mutation. Please note that patients with H3 K27M or *BRAF* mutations are ineligible for this study. Both strata will receive the same treatment regimen as described below. Please note Stratum 1 was closed to accrual on January 24, 2020.

Radiation therapy (RT) will be given in standard fractions (dose 54 to 59.4 Gy) over 6–7 weeks. During radiation, patients will receive veliparib concurrent with RT (Chemoradiotherapy), followed by a 4 week rest period. Four weeks after completion of RT, patients will start veliparib and oral temozolomide (Maintenance chemotherapy). Maintenance chemotherapy will continue for up to 10 cycles in the absence of progressive disease and unacceptable toxicities.

**IMPORTANT NOTE:** Patients must begin protocol therapy within 31 days of definitive surgery. If circumstances require, starting veliparib may be delayed up to 3 days if necessary, but veliparib must start no later than Day 34 after surgery and no later than the 4th day of RT (see [Section 3.3.5](#), [Section 4.1.1](#), and [Section 8.2](#)).

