**Temozolomide: PO**

Days: 1–5

Dose: 135 mg/m^2/dose once daily

Temozolomide should be administered 60-120 minutes after the veliparib dose and should be given consistently around the same time every day.

**Note:** Temozolomide doses should be rounded to the nearest 5 mg capsule size (see [Appendix VIII](#) for suggested capsule formulation dosing tables). For patients unable to swallow capsules, the capsules can be opened and mixed with apple sauce or apple juice, which should be used immediately after mixing (preferred) or must be used in 2 hours after mixing (see [Section 6.2](#) and [Appendix V](#)).

If emesis occurs within 15 minutes of taking a dose of temozolomide, then the dose may be repeated once. If emesis occurs after 15 minutes, the dose should not be repeated. Instructions for administration of oral temozolomide to young children are included in [Appendix V](#).

Disease evaluations should occur prior to every odd number of Maintenance cycle (see [Section 4.5.2](#)) for details).

See [Section 5.0](#) for Dose Modifications based on Toxicities.

Following completion of Cycle 1 of Maintenance chemotherapy, subsequent cycles will start on Day 29 or when criteria to begin the next cycle are met, whichever occurs later, absent disease progression or unacceptable toxicity.

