4.5.2 Required Observations in Maintenance Chemotherapy – Cycles 2–10

- a. Physical exam
- b. Height, weight
- c. Performance status: Prior to each odd-numbered cycle of Maintenance chemotherapy (e.g., Cycle 1, Cycle 3, Cycle 5, etc.)
- d. CBC/diff/platelets: Obtain weekly
- e. Bilirubin, Creatinine
- f. AST/ALT
- g. Brain MRI: Prior to each odd-numbered cycle of Maintenance chemotherapy (e.g., Cycle 3, Cycle 5, etc.)

**This listing only includes evaluations necessary to answer the primary and secondary aims. OBTAIN OTHER STUDIES AS REQUIRED FOR GOOD CLINICAL CARE.**

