#### 4.5.3 Maintenance Chemotherapy Treatment Details – Cycles 2–10

Each cycle of Maintenance chemotherapy lasts 28 days.

*Criteria to start Cycle 2 and subsequent cycles:*

- Absolute neutrophil count (ANC)  $\geq$  750/ $\mu$ L
- Platelet Count  $\geq$  75,000/ $\mu$ L (without transfusion within the last 7 days)
- Serum creatinine  $\leq$  1.5 x ULN
- Total bilirubin  $\leq$  1.5 x ULN, ALT  $<$  2.5 x ULN, AST  $<$  2.5 x ULN
- The patient has no evidence of progressive disease (see [Section 10.4](#)) as assessed clinically and/or by imaging studies.

Disease evaluations should occur prior to every odd number of Maintenance cycle (see [Section 4.5.2](#)) for details).

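### Section 10.4 names the pre-Cycle 3 MRI as the example both of scans within 3 months of radiotherapy and of scans beyond 3 months; on schedule it is done by day 84, so the second naming is wrong

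*Combined protocol and SAP*

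**What the plan says.** Section 10.4 first gives the standard definition of progressive disease (PD). It then makes an exception because RT can cause "transient, reversible swelling during or within the first 3 months after completion of RT". For MRIs in that period, local growth of 25% to under 50% in area, with no new lesions, is not PD. The scans meant are named: "i.e., on the required MRI 4 weeks after completing RT, or the scan performed prior to Cycle 3 of the Maintenance". A removal sentence follows: "Thus, during and for 3 months after completion of RT, patients should only be removed from protocol therapy for progressive disease" if area has grown by at least 50% or a new lesion appears beyond the radiation port.

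The next paragraph says that the standard criteria take over with required scans "done more than 3 months after completion of RT (i.e., prior to Cycle 3 of therapy", or with scans for suspected progression after that time.

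The schedule is set elsewhere:

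- Section 4.1: "Four weeks after completion of RT, patients will start veliparib and oral temozolomide".
- Section 4.1.2: cycles of 28 days.
- Section 4.4.3: "subsequent cycles will start on Day 29 or when criteria to begin the next cycle are met, whichever occurs later".
- Section 4.5.2: "Brain MRI: Prior to each odd-numbered cycle of Maintenance chemotherapy (e.g., Cycle 3, Cycle 5, etc".

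Section 4.5.3 makes it a condition of starting Cycle 2 and every later cycle that "The patient has no evidence of progressive disease". Section 8.1 lists PD as a ground for removal from protocol therapy.

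**The concern.** One scan is offered as the example of two windows that cannot overlap, and both parentheticals are introduced as explanations of what the window means. A site that works from named visits can find support for either rule on the pre-Cycle 3 scan.

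That scan decides whether Cycle 3 starts. A site that follows the second parenthetical could take an on-schedule patient off protocol therapy for the post-RT swelling that the exception exists to tolerate. Section 16.1 leaves response assessment to the sites. Central imaging review is retrospective and its results are not returned, so it cannot reverse a removal when it happens.

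**Working it through.** **1. Check the plan's own anchor.** Section 4.1.2 puts the start of Maintenance at about Week 11. Counting from a Monday start at five fractions a week:

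- 30 fractions end on study day 5 × 7 + 5 = 40; adding 28 gives day 68, in Week 10.
- 33 fractions end on study day 6 × 7 + 3 = 45; adding 28 gives day 73, in Week 11.

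This agrees with the stated figure.

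**2. Date the pre-Cycle 3 scan, in days after the last fraction.**

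- Cycle 1 Day 1: 28.
- Cycle 3 Day 1: 28 + 2 × 28 = 84. The scan precedes it, so it is done at or before day 84.
- With the 72-hour scheduling allowance in Section 4.0: 84 + 3 = 87.
- Rounding Cycle 1 to a Monday or to Week 11 moves Cycle 3 Day 1 to between days 82 and 89.

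**3. Compare with 3 months.** The protocol gives no number of days. Three calendar months span 89 to 92 days, so every on-schedule variant in step 2 is within 3 months. The first scheduled MRI beyond 3 months precedes Cycle 5: 28 + 4 × 28 = day 140.

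**4. Allow for delay.** From day 84, the scan leaves the window once cycle delays total more than 89 − 84 = 5 to 92 − 84 = 8 days. Section 5.3.1.2.3 allows a hematologic delay of up to 21 days per subsequent cycle.

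- One such delay: 84 + 21 = day 105.
- Two such delays: 84 + 42 = day 126.

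Day 126 is not a ceiling. Cycle 1 has its own start criteria and can itself be late. In these cases the first parenthetical is the wrong one.

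**5. Set the two rules side by side on this scan.**

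| Finding | Rule within 3 months | Standard rule |
|---|---|---|
| Growth of 25% to under 50%, no new lesions | Not PD | PD |
| Smaller growth with neurologic worsening not otherwise explained | Not a ground under the removal sentence | PD |
| New lesion inside the radiation port | Arguably not a ground for removal | PD |
| Growth of 50% or more | PD | PD |
| New lesion outside the port | PD | PD |

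The third row is arguable because the enlargement exception requires no new lesions at all, while the removal sentence mentions only those outside the port.

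**6. Treatment forgone.** Removal at this scan follows two cycles, so at most 10 − 2 = 8 Maintenance cycles are lost.

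**The case against.** The strongest reply is that the operative rule is already a date rule. Section 10.4 gives the time test three times, and the removal sentence uses time alone without naming a scan. Anyone who knows the RT end date can classify any scan, and the stated purpose of the exception points the same way. On that view the second parenthetical is a slip in an example. Most of this stands: the date reading is the better one. But the text never says that the date overrides the named scan, and the slip sits in the rule that controls removal.

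A second reply is that 89 to 92 days is my reading of 3 months. Section 17.11 divides failures at 12 weeks after RT, which is 12 × 7 = 84 days. The protocol does not equate the two. If it did, a scan done by day 84 would still be inside the window, but with no slack: the 72-hour allowance could put it outside, and the 5-to-8-day margin would vanish.

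A reader might go further and infer that EFS is biased, or that the Stratum 2 analysis, planned on 13 events, is compromised. The documents do not support that. EFS events are not itemised, so the step from a site's PD call to an EFS event is an inference. The number of affected scans is unknown, and some early growth will be true progression. Retrospective central review also leaves a means of checking calls, although the protocol does not say that it determines EFS.

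**Conclusion.** The inconsistency is real and is in current text. For on-schedule patients the second parenthetical is wrong; for sufficiently delayed patients the first is. A named scan cannot stand in for the date in either place.

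The scope is one scan and the first three rows of the table. For an affected on-schedule patient the cost is up to 8 Maintenance cycles. If an event were also recorded, it would be dated nominally 140 − 84 = 56 days before the next required scan. Unscheduled scans could shorten that gap, and an event might never be recorded if the swelling resolved.

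This rests on the nominal 4-week rest and 28-day cycles, and on 3 months meaning calendar months. It would be too strong to say that the protocol contains two incompatible progression rules: there is one date rule with a mislabelled example. No direction of bias and no effect on hazard ratio, power or type I error is shown. It should be corrected because it governs treatment removal and the correction is cheap.

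**What to change.** - In the second parenthetical of Section 10.4, replace Cycle 3 with Cycle 5. On schedule the two paragraphs then agree.
- Add one sentence: time from completion of RT governs, whichever scan is named. This covers delayed patients and a late Cycle 1.
- Give 3 months as a fixed number of days or weeks. The choice is the sponsor's and should take account of the 12-week cut in Section 17.11. A scan done by day 84 is inside under 12 weeks or under 13 weeks (91 days), but 12 weeks leaves no room for a scan taken late within the 72-hour allowance.

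Going forward this is a change of wording, with no new data and no change in who assesses progression. Looking back there is some work. The trial was activated in 2018, so PD calls at the pre-Cycle 3 scan may already exist. Each should be checked against the RT end date and the measurements and lesion findings on file, with a scan re-read only where those records are insufficient.
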